#### **15.4 Analysis of Secondary Endpoints**

Parameters such as maximum plasma concentration (Cmax) and time to Cmax (Tmax) will be determined from the observed data. The terminal elimination rate constant (ke) will be obtained using linear regression of log transformed concentrations over the terminal log-linear decline phase. Oral clearance (CL/F) will be calculated using Dose/AUC $0-\infty$ .

#### **15.5 Interim analysis**

There is no scheduled interim analysis, as the trial is short in duration, but serious adverse events will be monitored by the committee on an ongoing basis throughout the study.

#### **15.6 Sample Size and Randomization**

Using a paired t-test and prior data, a sample size of n=10 in each group is needed to detect a 50% difference in AUC $0-12$  between the two study regimens with a statistical power of 80% (two sided alpha = 0.05) and standard deviation of 50%. Due to the lesser effects of rifampin on fluvastatin AUC, the within subject variability can affect the sample size. We plan to enroll sample size of 12 subjects to maintain an adequate sample size in case of potential attrition.

Once included in the study, patients will be randomized using computer-generated random numbers, corresponding to each treatment. This will be performed by someone other than the investigator and will ensure equal number of patients in each treatment sequence.

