### 1.2 Overview of Clinical Studies

Contrary to our expectations, one clinical study has demonstrated that co-administration of single-dose rifampin with 2 mg of fluvastatin results in significant increase in exposure of the cholesterol-lowering agent. However this study was conducted with one tenth to one

fortieth of the common dose of fluvastatin, and we believe that the effect of rifampin on fluvastatin exposure in this study to be due to the low concentration of fluvastatin.

Clinical studies have demonstrated that co-administration of single-dose rifampin with the BDDCS Class II drug atorvastatin results in marked increases in concentrations of the cholesterol-lowering agent. Similar studies with the BDDCS class III drug rosuvastatin and class II drug glyburide showed similar transporter effects which increased plasma concentrations of the two drugs when co-administered with a single dose of rifampin. These studies have demonstrated the significant effects of hepatic uptake transporters on the pharmacokinetics of BDDCS class II and III drugs. It is expected that these transporter effects will not be significant for BDDCS class I drugs like fluvastatin.

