## 2 STUDY RATIONALE

Characterizing the effect of inhibition of hepatic uptake transporters by rifampin, on the pharmacokinetics of fluvastatin will advance our understanding of statin clinical pharmacology. It will give us a better understanding of the effects of hepatic uptake transporters on statin pharmacokinetics, statin drug-drug interaction and will serve as a validation check for the BDDCS classification system.

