## 3 STUDY OBJECTIVES

### 3.1 Primary Objective

The primary objective is to determine whether or not inhibition of OATP1B1-mediated drug transport of fluvastatin will be clinically significant. The study will assess if a IV dose of rifampin (to inhibit hepatic uptake transporters) immediately prior to oral fluvastatin dosing will have any effect on fluvastatin total drug exposure.

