### 1.2 Overview of Clinical Studies

Clinical studies have demonstrated that co-administration of single-dose rifampin with the BDDCS Class II drug atorvastatin results in marked increases in concentrations of the cholesterol-lowering agent. Similar studies with the BDDCS class III drug rosuvastatin and class II drug glyburide showed similar transporter effects which increased plasma concentrations of the two drugs when co-administered with a single IV dose of rifampin. These studies have demonstrated the significant effects of hepatic uptake transporters on the

pharmacokinetics of BDDCS class II and III drugs. It is expected that these transporter effects will not be significant for BDDCS class I drugs like fluvastatin.

Contrary to this expectation, one clinical study has demonstrated that co-administration of single-dose rifampin with 2 mg of fluvastatin results in significant increase in exposure of the cholesterol-lowering agent. However this study was conducted with one tenth to one fortieth of the common dose of fluvastatin, and we believe that the effect of rifampin on fluvastatin exposure in this study to be due to the low concentration of fluvastatin.

Clinical studies have demonstrated that the effects of hepatic OATP1B1 transporters on the BDDCS Class II drug glyburide are the same under induced and non-induced conditions. Concomitant rifampin treatment under the the induced condition yielded a glyburide AUCIVrif:AUCnoIVrif ratio of 2.06, which is comparable to the AUC ratio of 2.18 under the non-induced condition, despite the lower absolute AUC values in the CYP enzyme induced cohort. For fluvastatin (at clinical doses), it is expected that this AUCIVrif:AUCnoIVrif will be closer to 1, and it is desired to compare these ratios between induced and uninduced states as has previously been done for glyburide.

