## 3. STUDY OBJECTIVES

### 3.1 Primary Objective

The primary objective is to determine whether or not inhibition of OATP1B1-mediated drug transport of fluvastatin will be clinically significant when hepatic enzymes are induced.

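### The p<0.05 rule cannot support a finding of no clinically significant effect, the answer both protocols expect, because no interval for the AUC ratio and no limit for clinical significance is planned

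*Combined protocol and SAP*

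**What the plan says.** The file holds two protocols, one for single-dose rifampin and one for the hepatically induced state. Their statistical sections are nearly the same.

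- **Objective (Section 3.1).** The single-dose protocol states: "The primary objective is to determine whether or not inhibition of OATP1B1-mediated drug transport of fluvastatin will be clinically significant". A second sentence there asks, more simply, whether rifampin changes total fluvastatin exposure at all. The induced-state protocol has only the first question, whether the inhibition "will be clinically significant when hepatic enzymes are induced".
- **Expected result.** Section 1.2 of both protocols says: "It is expected that these transporter effects will not be significant for BDDCS class I drugs like fluvastatin". Only the induced-state protocol puts this as a ratio: after quoting glyburide AUC ratios of 2.06 and 2.18, it expects that the fluvastatin ratio "will be closer to 1, and it is desired to compare these ratios" between states. Section 2 of the single-dose protocol adds that the study "will serve as a validation check for the BDDCS classification system".
- **Sizing (Section 15.6, both).** By a paired t-test, "a sample size of n=10 in each group is needed to detect a 50% difference in" AUC0-12, "with a statistical power of 80% (two sided alpha = 0.05) and standard deviation of 50" percent. Twelve are enrolled to allow for attrition. The same paragraph says: "Due to the lesser effects of rifampin on fluvastatin AUC, the within subject variability can affect the sample size".
- **Analysis (Section 15.3 and synopsis, both).** Log-transformed parameters are compared by repeated-measures ANOVA, and differences are also taken to a paired t-test. Significance is p<0.05. Data are shown as means with standard deviations.

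Neither protocol mentions a confidence interval, and neither defines clinical significance as a size of AUC change. Section 15 promises a detailed SAP before the final analysis but commits it to neither item. No separate SAP is among the documents.

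**The concern.** The question is about the size of an effect, and the rule is about whether an effect can be detected. If p<0.05, the trial has shown some effect but has no stated standard for calling it clinically significant. If p≥0.05, which is what the protocols expect, the natural reading is that inhibition is not clinically significant and that the classification system has passed its check. A non-significant test does not show that. It also occurs when variability is high or the sample is small, so more noise makes the expected answer more likely. Without an interval and a limit set in advance, the plan as written does not separate a result that excludes a relevant effect from one that is merely imprecise.

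**Working it through.** **Inputs.** Difference 50%, SD 50%, two-sided alpha 0.05, power 80%, n=10, 12 enrolled: all from Section 15.6. The section does not say whether the SD is that of the paired differences or of each treatment, or on which scale. I read it as the SD of the paired differences, as a percentage of the control mean, because that reproduces the stated n.

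**1. The plan's own figure.** Standardised effect d = 0.50/0.50 = 1.0. Power is the probability that a noncentral t variable with n−1 degrees of freedom and noncentrality d√n lies beyond ±t(0.975, n−1).
- n=9: 74.8%
- n=10: 80.3%
- n=12: 88.3%

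So n=10 is the smallest number giving 80%, and the figure is reproduced.

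**2. Precision on the same inputs.** The 95% half-width is t(0.975, n−1) × 0.5/√n when the observed SD is 50%.
- n=10: 2.262 × 0.5/√10 = 0.358, about 36 percentage points
- n=12: 2.201 × 0.5/√12 = 0.318, about 32 percentage points

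A result just short of significance could then carry an observed change of up to 36% (n=10) or 32% (n=12), with a 95% limit at twice that: 72% or 64%.

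**3. How often a real change gives p≥0.05.** The same formula with d = change/0.50. Only the 50% row is a figure from the documents; the other rows are illustrations.

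| True change | n=10 | n=12 |
|---|---|---|
| 25% | 71% | 65% |
| 30% | 60% | 53% |
| 40% | 38% | 29% |
| 50% (design value) | 20% | 12% |

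**4. Sensitivity to the SD.** If 50% were the SD of each treatment, the SD of the difference would be 0.5 × √(2(1−ρ)), with ρ the within-subject correlation. At ρ=0.5 nothing changes. Over ρ from 0 to 0.8 the rate of p≥0.05 at a true 30% change runs from 78% to 24% (n=10) and from 73% to 15% (n=12). On the log scale, with an assumed log-difference SD of 0.5, a true ratio of 1.3 gives p≥0.05 in 68% (n=10) or 62% (n=12).

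**5. Could 10–12 subjects support a conclusion of no relevant effect?** That needs the whole 90% interval inside ±θ, so I computed the probability that |mean difference| + t(0.95, n−1) × SD/√n is below θ, at a true difference of zero. On the percentage scale with SD 50%:

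| θ | n=10 | n=12 |
|---|---|---|
| ±25% | 7% | 11% |
| ±30% | 18% | 27% |
| ±40% | 52% | 66% |
| ±50% | 80% | 89% |

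The planned analysis is on the log scale, where the answer depends heavily on an SD that the protocols do not give. With 12 subjects, illustrative limits of 0.69 to 1.45 and a true ratio of 1, the chance is 86%, 56% or 19% for an assumed log-difference SD of 0.385, 0.5 or 0.668. So whether 12 is enough cannot be settled from the documents.

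**The case against.** The strongest reply has four parts.

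**The test fits part of the objective.** The second sentence of Section 3.1 in the single-dose protocol asks about any effect on exposure, and a difference test addresses that. This stands, and the test should stay. It does not cover the first sentence, and the induced-state protocol has only that first question.

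**The 30% is arbitrary.** It is. It appears nowhere in the documents, and at the design difference of 50% the rate of p≥0.05 is the intended 20% or 12%. The point does not rest on 30%: with no threshold stated, p≥0.05 fails to support the conclusion at any threshold.

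**The trial is not too small.** A reader might infer from the table in step 3 that it is. The documents do not support that. Taking the 50% design difference as the limit, the 90% interval would fall inside it in 80% (n=10) or 89% (n=12) of trials if there were no effect, and Section 12.3 replaces subjects who withdraw, so 12 completers is realistic. Adequacy depends on a limit and a log-scale SD that are not stated. Equally, no assurance can be given that 12 is enough.

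**The later SAP may supply the interval.** It may, and the planned data allow it without redesign. But a limit for clinical significance chosen after data collection would carry less weight, and Section 15 does not commit to one.

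A reader might also say that both protocols predict a ratio near 1. Only the induced-state protocol uses a ratio, and its wording is comparative, set against glyburide. The single-dose protocol expects only that effects will not be significant.

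**Conclusion.** The point holds as a gap of moderate severity in the analysis and decision rule of both protocols. The primary question is clinical significance, the expected answer is little or no effect, and the only rule is a difference test that cannot establish that answer. The sizing calculation is correct for what it claims. Reading the SD as that of the paired differences, the plan leaves a 95% uncertainty of about ±36 (n=10) or ±32 (n=12) percentage points around the AUC change, and it does not undertake to report it. The p≥0.05 rates for changes smaller than 50% are illustrations resting on that SD reading and on true changes chosen for the purpose.

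**What to change.** In Section 15.3 and the synopsis of both protocols:

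1. Make the primary result the geometric mean AUC0-12 ratio (rifampin plus fluvastatin to fluvastatin alone) with its 90% confidence interval from the log-scale crossover analysis. AUC0-12 is the measure used for sizing. Keep the planned p<0.05 test for the question of any effect.
2. State in advance, with a justification, the ratio limits within which the effect is regarded as not clinically significant. The values are for the sponsor to choose.
3. Conclude that the effect is not clinically significant only if the whole 90% interval lies inside those limits. State that p≥0.05 alone does not support that conclusion. Otherwise report the estimate and interval without the claim.

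In Section 15.6, give the log-scale precision that 12 subjects provide, or the chance of meeting the criterion in item 3, using the within-subject SD from the prior data that the section mentions.

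A mirror rule, requiring the interval to lie wholly outside the limits before an effect is declared, is not advised. On the percentage scale at the 50% design difference, it would succeed in only about 9% of trials with limits of ±45% and 5% with ±50%.

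The cost is text in two sections and the synopsis of each protocol, with no new samples or assays. The downside is that a null p-value may have to be reported as inconclusive.

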### **16 DATA COLLECTION, RETENTION AND MONITORING**

#### **16.1 Data Collection Instruments**

The Investigator will prepare and maintain adequate and accurate source documents designed to record all observations and other pertinent data for each subject treated with the study drug. The investigator will enter data from source documents corresponding to a subject's visit into the protocol-specific electronic Case Report Form (eCRF) when the information corresponding to that visit is available.

The Investigator is responsible for all information collected on subjects enrolled in this study. All data collected during the course of this study must be reviewed and verified for completeness and accuracy by the Investigator. A copy of the CRF will remain at the Investigator's site at the completion of the study.

## **16.2 Data Management Procedures**

The data will be entered into a validated database. The Data management group will be responsible for data processing, in accordance with procedural documentation. Database lock will occur once quality assurance procedures have been completed.

All procedures for the handling and analysis of data will be conducted using good computing practices meeting FDA guidelines for the handling and analysis of data for clinical trials.

## **16.3 Data Quality Control and Reporting**

After data have been entered into the study database, a system of computerized data validation checks will be implemented and applied to the database on a regular basis. The study database will be updated in accordance with the resolved queries. All changes to the study database will be documented.

## **16.4 Archival of Data**

The database is safeguarded against unauthorized access by established security procedures; appropriate backup copies of the database and related software files will be maintained. Databases are backed up by the database administrator in conjunction with any updates or changes to the database.

At critical junctures of the protocol (e.g., production of interim reports and final reports), data for analysis is locked and cleaned per established procedures.

## **16.5 Availability and Retention of Investigational Records**

The Investigator must make study data accessible to the monitor, other authorized representatives of the Sponsor (or designee), IRB/IEC, and Regulatory Agency (e.g., FDA) inspectors upon request. A file for each subject must be maintained that includes the signed Informed Consent, HIPAA Authorization and Assent Form and copies of all source documentation related to that subject. The Investigator must ensure the reliability and availability of source documents from which the information on the CRF was derived.

All study documents (patient files, signed informed consent forms, copies of CRFs, Study File Notebook, etc.) must be kept secured for a period of two years following marketing of the investigational product or for two years after centers have been notified that the IND has been discontinued. There may be other circumstances for which the Sponsor is required to maintain study records and, therefore, the Sponsor should be contacted prior to removing study records for any reason.

## **16.6 Monitoring**

Monitoring visits will be conducted by representatives of the Sponsor according to the U.S. CFR Title 21 Parts 50, 56, and 312 and ICH Guidelines for GCP (E6). By signing this protocol, the Investigator grants permission to the Sponsor (or designee), and appropriate regulatory authorities to conduct on-site monitoring and/or auditing of all appropriate study documentation.

## **16.7 Subject Confidentiality**

Only the investigators listed on this application and research personnel directly involved in the study will have access to personal information. All personal and medical data will be considered confidential. All subject information will be kept confidential as possible under the law.

## **17 ADMINISTRATIVE, ETHICAL, REGULATORY CONSIDERATIONS**

The study will be conducted according to the Declaration of Helsinki, Protection of Human Volunteers (21 CFR 50), Institutional Review Boards (21 CFR 56), and Obligations of Clinical Investigators (21 CFR 312).

To maintain confidentiality, all laboratory specimens, evaluation forms, reports and other records will be identified by a coded number and initials only. All study records will be kept in a locked file cabinet and code sheets linking a patient's name to a patient identification number will be stored separately in another locked file cabinet. Clinical information will not be released without written permission of the subject, except as necessary for monitoring by the FDA. The Investigator must also comply with all applicable privacy regulations (e.g., Health Insurance Portability and Accountability Act of 1996, EU Data Protection Directive 95/46/EC).

### **17.1 Protocol Amendments**

Any amendment to the protocol will be written by the investigator. Protocol amendments cannot be implemented without prior written IRB/IEC approval except as necessary to eliminate immediate safety hazards to patients. A protocol amendment intended to eliminate an apparent immediate hazard to patients may be implemented immediately, provided the IRBs are notified within five working days.

### **17.2 Institutional Review Boards and Independent Ethics Committees**

The protocol and consent form will be reviewed and approved by the IRB/IEC of each participating center prior to study initiation. Serious adverse experiences regardless of causality will be reported to the IRB/IEC in accordance with the standard operating procedures and policies of the IRB/IEC, and the Investigator will keep the IRB/IEC informed as to the progress of the study. The Investigator will obtain assurance of IRB/IEC compliance with regulations.

Any documents that the IRB/IEC may need to fulfill its responsibilities (such as protocol, protocol amendments, Investigator's Brochure, consent forms, information concerning patient recruitment, payment or compensation procedures, or other pertinent information) will be submitted to the IRB/IEC. The IRB/IECs written unconditional approval of the study protocol and the informed consent form will be in the possession of the Investigator before the study is initiated. The IRB/IECs unconditional approval statement will be transmitted by the Investigator prior to the shipment of study supplies to the site. This approval must refer to the study by exact protocol title and number and should identify the documents reviewed and the date of review.

Protocol and/or informed consent modifications or changes may not be initiated without prior written IRB/IEC approval except when necessary to eliminate immediate hazards to the patients or when the change(s) involves only logistical or administrative aspects of the study. Such modifications will be submitted to the IRB/IEC and written verification that the modification was submitted and subsequently approved should be obtained.

The IRB/IEC must be informed of revisions to other documents originally submitted for review; serious and/or unexpected adverse experiences occurring during the study in accordance with the standard operating procedures and policies of the IRB; new information that may affect adversely the safety of the patients of the conduct of the study; an annual update and/or request for re-approval; and when the study has been completed.

### **17.3 Informed Consent Form**

Informed consent will be obtained in accordance with the Declaration of Helsinki, ICH GCP, US Code of Federal Regulations for Protection of Human Subjects (21 CFR 50.25[a,b], CFR 50.27, and CFR Part 56, Subpart A), the Health Insurance Portability and Accountability Act (HIPAA, if applicable), and local regulations.

The Investigator will prepare the informed consent form, assent and HIPAA authorization and provide the documents to the Sponsor or designee for approval prior to submission to the IRB/IEC. The consent form generated by the Investigator must be acceptable to the Sponsor and be approved by the IRB/IEC. The written consent document will embody the elements of informed consent as described in the International Conference on Harmonisation and will also comply with local regulations. The Investigator will send an IRB/IEC-approved copy of the Informed Consent Form to the Sponsor (or designee) for the study file.

A properly executed, written, informed consent will be obtained from each subject prior to entering the subject into the trial. Information should be given in both oral and written form and subjects (or their legal representatives) must be given ample opportunity to inquire about details of the study. If appropriate and required by the local IRB/IEC, assent from the subject will also be obtained. If a subject is unable to sign the informed consent form (ICF) and the HIPAA authorization, a legal representative may sign for the subject. A copy of the signed consent form (and assent) will be given to the subject or legal representative of the subject and the original will be maintained with the subject's records.

